#### SPECIFIC AIMS/OBJECTIVES

- To determine the impact of Omegaven® on reversal of conjugated hyperbilirubinemia
- To determine the impact of Omegaven® on the prevention of essential fatty acid deficiency
- To determine the impact of Omegaven® administration on serum triglyceride
- To determine the impact of Omegaven® administration on coagulation profiles

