In a recent article by Lee et al, entitled "Impact of fish oil-based lipid emulsion on serum triglyceride, bilirubin, and albumin levels in children with parenteral nutrition-associated liver disease", published in Pediatric Research (December, 2009), the authors demonstrated that substituting fish oil-based lipid emulsion for the standard soybean-based emulsion will result in normalizing, to some degree, the altered physiologic balance that comes to exist in patients dependent on PN. The indices that have shown improvement were decreasing direct bilirubin and triglyceride levels and increasing albumin levels. In previous publications, these authors have also noted that the provision of fish-oil-based fat emulsion was not associated with essential fatty acid deficiency, hypertriglyceridemia, coagulopathy, infections, or growth delay.

Researchers at The Hospital for Sick Children, Toronto, Canada published their findings of their experience with Omegaven® in young children in a recent publication (February, 2009) The median age was 7.5 (range 3.6-46) months, and median parenteral nutrition duration before starting Omegaven® was 28.4 (range 15.3-55.3) weeks. Median initial serum conjugated bilirubin was 137 (range 54-203) micromole/L (8.06 [3.18-11.94] mg/dL). Nine of the twelve patients had complete and sustained resolution of hyperbilirubinemia within a median of 24 (range 7-37) weeks, and all were no longer being considered for liver transplantation. Improvements in markers of hepatic inflammation as well as nutritional status also were noted in these patients. Three of the 12 patients received a liver-intestine transplant while taking Omegaven®. There were no complications attributable to Omegaven®.

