## **DESIGN AND METHODS**

## Study Design

This phase II clinical trial will be a non-randomized, open-labeled, prospective study of intravenously administered Omegaven® fat emulsion in the treatment of PN associated liver injury.

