# **Recruitment Methods**

With an anticipated enrollment of 3-5 patients per year, 20-25 patients will be recruited over the course of the 5 year study.

Patients in the trial will be recruited from the NICU, PICU, CVICU, surgery, gastroenterology, and general pediatrics services at Levine Children's Hospital (LCH). Approximately 5-8 patients/year are diagnosed with severe PN associated liver injury at Levine Children's Hospital. The Principal Investigator ([name]) or Co-investigators ([name], [name]) will discuss treatment options including study treatment with the parents or legal guardians. Informed consent for participation in the study will only be obtained by physicians who are able to fully inform the patients of alternatives to participation. If the patient is a minor but of sufficient age and understanding, patient assent will also be obtained.

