#### **Dose Modification**

Hypertriglyceridemia:

If hypertriglyceridemia develops, defined as serum triglyceride levels > 200 mg/dL, the following will be considered prior to reducing the dose:

- a) If the level was obtained while the patient was receiving a continuous 24- hour infusion of Omegaven®, the total dose should be infused over 20 hours, and a repeat serum triglyceride level obtained prior to resuming the infusion 4 hours later.
- b) Other sources of hypertriglyceridemia should be considered and addressed (drugs, renal disease)

If necessary, if the triglycerides continue to remain high despite the aforementioned interventions, a dosage reduction of 25% will be considered.

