# **Definition of Primary and Secondary Outcomes/Endpoints**

The primary outcome is normalization of direct bilirubin to less than 0.4mg/dL by 9 months.

Seconday outcomes include:

- Omegaven® will prevent EFA deficiency as evidenced by normal EFA profiles on monthly evaluations
- The rate of triglyceride levels > 400 mg/dL with Omegaven® will be similar to that seen with PN administered with soy oil IFE (conventional emulsion, i.e., Intralipid®) as evidenced by baseline data and then weekly and monthly evaluations
- PN containing Omegaven® will be safe for patients with respect to the risk of unexpected bleeding/coagulopathies as evidenced by weekly and monthly evaluations

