## **Data and Safety Monitoring Plan**

Monitoring for toxicity due to Omegaven will be assessed by analyzing clinical and laboratory parameters including serum electrolytes, hematological studies, serum triglycerides, total cholesterol, essential fatty acid profiles, blood and urine glucose and liver and renal function tests. Blood samples will be taken prior to the start of therapy, and weekly thereafter until direct bilirubin <2mg/dL. Subsequent testing will be determined based on direct bilirubin values (as this is the monitoring standard of care for liver failure) and will be bimonthly or monthly. See Table 2 for additional information. Dose reduction will occur if there is evidence of hypertriglyceridemia (serum triglycerides > 200mg/dL), hyperglycemia (serum glucose >250mg/dL), or evidence of bleeding. Growth indices including weight, length/height, and head circumference will also be monitored. [name], the director of Pediatric Gastroenterology at LCH will be the Data and Safety Monitor. He will review patient data quarterly to ensure patient safety is upheld and that protocols are followed as described. The study will be halted in the event of one life threatening episode related to Omegaven® administration.

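### Aim 3 asks for the impact on serum triglyceride, but its only listed outcome is a > 400 mg/dL rate to be found 'similar' to soy oil, with no margin or reference rate

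*Protocol*

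**What the plan says.** Under Specific Aims/Objectives, the third aim is "To determine the impact of Omegaven® administration on serum triglyceride". It names no threshold.

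Under Definition of Primary and Secondary Outcomes/Endpoints, one item concerns triglyceride: "The rate of triglyceride levels > 400 mg/dL with Omegaven® will be similar to that seen with PN administered with soy oil IFE", to be judged "as evidenced by baseline data and then weekly and monthly evaluations". The section gives no margin for similarity, no expected rate on soy oil, and no test.

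Study Design describes a "non-randomized, open-labeled, prospective study", so there is no concurrent soy-oil group and the baseline data have to serve as the comparator. On size, Recruitment Methods says "With an anticipated enrollment of 3-5 patients per year, 20-25 patients will be recruited over the course of the 5 year study".

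Triglycerides are marked in all four columns of the laboratory monitoring table, including baseline. The Data and Safety Monitoring Plan adds: "Blood samples will be taken prior to the start of therapy, and weekly thereafter until direct bilirubin <2mg/dL". The background cites earlier experience with fish-oil emulsion: "The indices that have shown improvement were decreasing direct bilirubin and triglyceride levels and increasing albumin levels". Dose Modification acts on hypertriglyceridemia, "defined as serum triglyceride levels > 200 mg/dL". Statistical Power and Sample Considerations states that the study does not aim to prove statistical significance.

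**The concern.** The aim concerns a continuous quantity that every child supplies before and during treatment. The outcome reduces it to whether a level passes 400 mg/dL. A child who moves from 150 to 300 mg/dL and a child who moves from 300 to 150 mg/dL count the same. The fall that the background leads one to expect can be seen only in children who start above 400 mg/dL.

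The wording also fixes the conclusion in advance. With neither a margin nor a reference rate, any result with few events fits 'similar', whether or not triglyceride changed. At stake is a report that the two emulsions are alike on triglyceride when the data could not have told them apart on this measure, while more informative data, already scheduled, have no stated place in the outcomes.

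**Working it through.** **Inputs from the protocol.** Single arm; 20-25 children planned; triglyceride at baseline and in each later monitoring column; cut-off 400 mg/dL. There is no sample-size calculation to reproduce. The accrual rate gives 3 × 5 = 15 to 5 × 5 = 25, so the upper figure of 25 agrees and is used below as the favourable case.

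**Assumptions (not in the protocol).** Log-normal triglyceride with soy-oil median m = 100 to 250 mg/dL and log SD s = 0.5 to 0.6; SD of the within-child log change σ = 0.4 to 0.6; two-sided 5% level; one baseline and one on-treatment value per child.

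**1. What zero events would show.** The exact two-sided 95% upper limit for 0 of n is 1 − 0.025^(1/n):
- n = 25: 13.7%
- n = 20: 16.8%

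A complete absence of events is therefore compatible with about one child in seven exceeding 400 mg/dL.

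**2. Minimum evidence on the binary scale.** The exact McNemar p-value when all k discordant children change in the same direction is 2 × 0.5^k. For k = 5 it is 0.0625; for k = 6 it is 0.031. So no fall can reach p < 0.05 unless at least 6 of 25 children (24%) start above 400 mg/dL. The chance of 6 or more, which is also the power if every such child falls below 400 and none rises above it, is 3% at a 10% baseline rate, 38% at 20% and 81% at 30%.

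**3. Power of paired > 400 status, n = 25.** The share above 400 is p₀ = 1 − Φ(ln(400/m)/s) on soy oil and p₁ = 1 − Φ(ln(400/(mR))/s) after a ratio change R. The within-child correlation is r = 1 − σ²/(2s²). With σ = 0.5:

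| Soy median m (mg/dL) | Share above 400 | Power, 25% fall (R = 0.75) | Power, one-third rise (R = 4/3) |
|---|---|---|---|
| 100 | 0.3-1.0% | under 0.1% | under 0.1% |
| 150 | 2.5-5.1% | under 0.1% | 0.6-1.7% |
| 200 | 8.3-12.4% | 0.6-1.7% | about 11% |
| 250 | 17-22% | 7-8% | 20-25% |

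The first three rows, with about 10% or fewer above 400 mg/dL, give the 0-11% range.

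**4. Power of the paired log change, n = 25.** The noncentrality is |ln 0.75| × √25 / σ = 0.288 × 5 / σ, with a critical t of 2.064 on 24 degrees of freedom. Since ln(4/3) is also 0.288, the one-third rise gives the same result.
- σ = 0.4: 3.60, power 93%
- σ = 0.5: 2.88, power 79%
- σ = 0.6: 2.40, power 63%

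At n = 20 the powers are 86%, 68% and 53%.

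**5. Precision instead of power.** With σ = 0.5 and n = 25, the 95% CI for the ratio runs from the estimate divided by to multiplied by exp(2.064 × 0.5/5) = exp(0.206) = 1.23. An estimated ratio of 0.75 would have limits of about 0.61 and 0.92.

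**6. Where the binary scale does work.** A rise from 5% to 40% above 400 mg/dL has 79-92% power at n = 25, and complete elimination from a 30% baseline has 81%.

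**The case against.** The strongest reply is that the protocol specifies no test, significance level or decision rule for this outcome, leaves the specific analysis to the statistician and disclaims significance. Low power against a McNemar test that nobody planned is then not a broken promise. This stands, and it is why the power figures above are illustrative. It does not rescue the outcome: the protocol still states a conclusion of similarity without saying what would count as similar, and for pure estimation a ratio with an interval says more than a handful of events.

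A rate of extreme values is also a legitimate safety measure, and was not written to demonstrate a fall. That stands too. The defect is that it is the only listed outcome for an aim about triglyceride as such.

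Third, the outcome counts repeated levels, not one pair per child. True, but this does not help. In a simulation with 20 on-treatment draws per child and within-child correlation 0.5, power for a fall was still about 4% or less. A test that ignored the clustering rejected about 23-24% of the time with no change at all.

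A reader might infer that Aim 3 cannot be answered, or that the outcome has almost no power whatever the truth. The documents support neither. The outcomes are introduced as a list that may not be exhaustive, the continuous values are collected, and a statistical analysis plan not seen here may use them. Rarity above 400 mg/dL on soy oil is an assumption: the action at 200 mg/dL and the cited experience bear on treated values, not on the baseline.

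**Conclusion.** The listed triglyceride outcome does not match the aim it serves, and its conclusion of similarity has neither a margin nor a reference rate. That follows from the text alone. So does the 13.7% upper limit for 0 of 25 by exact arithmetic.

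The size of the loss is conditional. With about 10% or fewer of the children above 400 mg/dL on soy oil, power at n = 25 for a 25% fall or a one-third rise is roughly 0-11% on the binary scale, against about 63-93% for the paired log change with SD 0.6 to 0.4. With a higher baseline share the gap narrows, and very large shifts would be seen either way. The continuous measure has limits too: a shift equivalent to moving from 5% to 10% above 400 mg/dL would have only 23-42% power (within-child correlation 0 to 0.5).

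This concerns one secondary outcome in a small uncontrolled study. It does not touch the primary outcome.

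**What to change.** In Definition of Primary and Secondary Outcomes/Endpoints, add as the outcome for Aim 3 the within-child change in log serum triglyceride from the pre-Omegaven baseline to one fixed early scheduled draw, for example week 4 with a stated window. Report it as a ratio with 95% CI and describe it as an uncontrolled before-after estimate. Week 4 falls within the 30 days of further PN that the inclusion criteria expect.

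Keep the rate above 400 mg/dL as a descriptive safety count with an exact interval. State whether it counts children or levels, and drop 'similar' as its conclusion.

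The cost is one added outcome and one reworded one, with no new patients. A child whose direct bilirubin falls below 2 mg/dL before week 4 leaves the weekly schedule, so the window must allow for this or one triglyceride value must be kept at that time.

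The change has downsides that should be stated with the result. Regression to the mean can produce an apparent fall. Action taken on levels above 200 mg/dL can alter later values. Draw frequency depends on bilirubin, so children with persistent cholestasis contribute more values, and a model over all draws should be supportive only.

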# **Statistical Power and Sample Considerations**

As discussed above, this study protocol is not intended to prove statistical significance.

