# RSKS AND DISCOMFORTS Description of Risks and Discomforts

Potential Risk of Omegaven® Treatment

Omegaven® has been studied in animal pre-clinical models as well as Phase I, II, III, and post marketing human trials in both Europe and Asia. Prolonged bleeding time and an inhibited platelet aggregation can occur. It should not be administered to patients known to be allergic to fish or egg protein.

Contraindications to Omegaven® include the following:

Impaired lipid metabolism
Severe hemorrhagic disorders
Unstable diabetes mellitus
Collapse and shock
Stroke/Embolism
Recent cardiac infarction
Undefined coma status
Known allergy to fish or egg protein

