#### Side effects:

The infusion of Omegaven® can lead to a prolonged bleeding time and an inhibited platelet aggregation. In rare cases, patients may experience a fishy taste.

The administration of Omegaven® should be stopped or reduced if there is a marked increased in blood glucose levels during the Omegaven® infusion. Undesirable effects that are seen during the infusion of Omegaven® that may also occur with conventional fat emulsions (i.e., Intralipid®) include:

Slight rise in body temperature
Heat sensation and/or cold sensation
Chills
Flushing or cyanosis
Lack of appetite, nausea, vomiting
Dyspnea
Headache, pain in the chest, bone pain
Priapism
Increase/decrease blood pressure
Anaphylactic reactions/erythema

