# Summary – Overall Risk Assessment

Patients will be at some risk inherent in taking a pharmaceutical agent that has not been fully evaluated for long duration treatment. However, the availability of safety data demonstrates no life-threatening risks or toxicities to vital organs or physiologic functions. Prolonged bleeding times and inhibition of platelet aggregation are a potential risk, especially to those patients with an underlying coagulopathy or those being treated with an anticoagulant. The potential benefits of Omegaven® in this patient population are mainly based on the experimental evidence; a highlighted case of dramatic success; and success in phase I clinical trials. However, the study will only be available to those for whom no standard therapy is available or appropriate, or has already failed. The risks and potential benefits will require careful individual assessment by both the investigators and patients. The heterogeneity of clinical manifestations will lead to non-uniform risk-benefit ratios across the eligible patient population.

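### The bleeding-safety outcome asserts safety on the strength of scheduled tests that do not assess the platelet-function risk the protocol names; clinical bleeding of any grade should be the counted outcome

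*Protocol*

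**What the plan says.** Under Definition of Primary and Secondary Outcomes/Endpoints, the third secondary outcome is that PN containing Omegaven "will be safe for patients with respect to the risk of unexpected bleeding/coagulopathies as evidenced by weekly and monthly evaluations". The matching aim under Specific Aims/Objectives is "To determine the impact of Omegaven® administration on coagulation profiles".

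The bleeding hazard is named in three places, each time as an effect on platelets:

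- Description of Risks and Discomforts: "Prolonged bleeding time and an inhibited platelet aggregation can occur".
- Side effects: the infusion "can lead to a prolonged bleeding time and an inhibited platelet aggregation".
- Summary – Overall Risk Assessment: "Prolonged bleeding times and inhibition of platelet aggregation are a potential risk". That section adds that children with an existing coagulopathy or on anticoagulants are especially exposed.

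The Laboratory Monitoring Schedule lists five haemostasis rows at every time point: platelets, PT, PTT, INR and fibrinogen. It has no row for bleeding time or platelet aggregation.

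The study is a "non-randomized, open-labeled, prospective study". On numbers, Recruitment Methods says "With an anticipated enrollment of 3-5 patients per year, 20-25 patients will be recruited over the course of the 5 year study". Statistical Power and Sample Considerations says that "this study protocol is not intended to prove statistical significance".

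**The concern.** The outcome is worded as a conclusion, and the evidence it cites does not match the hazard described elsewhere in the Protocol. A platelet count measures number. PT, PTT, INR and fibrinogen concern clotting factors. All five can be normal while platelet function is inhibited.

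With the planned procedures, the platelet effect could show itself only as clinical bleeding. The outcome does not make clinical bleeding a counted event, and no section asks about it at each evaluation. Followed literally, the trial could report safety on bleeding from tests insensitive to the stated mechanism, in too few children to exclude a substantial rate. Events that were never asked about cannot be recovered at the analysis stage.

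**Working it through.** **1. What the outcome's evaluations are.** The wording does not define them. The triglyceride outcome in the same list cites the same weekly and monthly cadence, and the fatty-acid outcome cites monthly checks. Both can only mean laboratory work. The Laboratory Monitoring Schedule runs at that kind of cadence: weekly, then bimonthly, then monthly. The laboratory reading is therefore the natural one, though not the only possible one.

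**2. Hazard against measurement.**

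| Part of the outcome or risk | Scheduled test | Addressed? |
|---|---|---|
| Coagulopathy | PT, PTT, INR, fibrinogen | Yes |
| Low platelet number | Platelet count | Yes |
| Bleeding time, platelet aggregation | None listed | No |
| Clinical bleeding | None; seen through adverse-event reporting | Not as the stated evidence for this outcome |

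**3. How bleeding is otherwise seen.** Adverse Event Criteria and Reporting Procedures relies on vital signs, physical examination, laboratory work, and observation by nurses and instructed guardians, and requires all adverse events to be recorded. The Data and Safety Monitoring Plan acts on evident bleeding. In the table of possible adverse events, however, the only clinical bleeding term is uncontrolled bleeding at grade IV; coagulopathy appears as a grade IV laboratory event. Description of Study Treatments says that home nurses and guardians are taught adverse-event monitoring from the table. A minor bleed has no listed term there.

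**4. Sample size.** The only planned figure is 20-25 children. The stated accrual gives 3 × 5 = 15 to 5 × 5 = 25, so the upper end reproduces and the lower end does not. The stated 20-25 is used below. There is no power or precision figure to reproduce.

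**5. What zero bleeds would show.** Assume every child is treated and none bleeds, the most favourable result. The exact upper limit is 1 − a^(1/n), with a = 0.025 for a two-sided 95% interval and a = 0.05 for a one-sided 95% limit. The Protocol states no level, so both are assumptions.

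| n | Two-sided 95% | One-sided 95% |
|---|---|---|
| 20 | 1 − 0.025^(1/20) = 16.8% | 1 − 0.05^(1/20) = 13.9% |
| 25 | 1 − 0.025^(1/25) = 13.7% | 1 − 0.05^(1/25) = 11.3% |

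**6. How often a real risk would go unseen.** The chance of no bleed is (1 − p)^n. The Protocol gives no background rate, so p is illustrative.

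- p = 10%: 0.90^20 = 12.2%; 0.90^25 = 7.2%.
- p = 5%: 0.95^20 = 35.8%; 0.95^25 = 27.7%.

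**The case against.** The strongest reply is that the evaluations need not be laboratory-only. The Data and Safety Monitoring Plan speaks of both clinical and laboratory parameters, adverse events are sought by examination and observation, and outpatients have clinical follow-up. The outcome itself names bleeding as well as coagulopathy. The panel also matches the aim, which concerns coagulation profiles; platelet function is disclosed as a risk and is not something the trial undertook to measure. All the secondary outcomes are phrased as expected results, the Protocol disclaims statistical proof, and any trial of this size has wide limits.

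Much of this stands. A reader might infer that bleeding would go unobserved; the documents do not support that, because overt bleeding is recorded as an adverse event. A reader might infer that normal results would trigger a formal declaration of safety; no such rule is stated. A reader might quote an upper limit of 21.8%; that requires n = 15, which follows only from the low accrual rate and is not the stated target. Nor is the lack of a named interval method an error, since a statistical analysis plan may supply it.

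What the reply does not remove is that the outcome gives a conclusion where a countable event should be, that the named hazard is outside the scheduled tests, and that bleeding below grade IV has no listed term and no scheduled question.

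**Conclusion.** The point holds in a limited form. The scheduled tests address the coagulopathy half of the outcome. They do not assess the platelet effect that the Protocol names three times, so normal laboratory results cannot support safety against it. Clinical bleeding is captured, but passively, and it is not the stated evidence for this outcome; under-recording of lesser bleeding is a possibility, not a demonstrated fact.

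A clean result would still be weak evidence: the data would remain compatible with a bleeding risk of up to 13.7-16.8% (two-sided) or 11.3-13.9% (one-sided). Those figures assume zero events, 20-25 treated children and a 95% level. They contradict no margin in the Protocol, because it states none. They show why an assertion of safety does not fit a single-arm study that disclaims proof, whereas a descriptive estimate does. This is a cheap improvement to a secondary outcome, not a flaw in the design.

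**What to change.** Restate the outcome as the number and proportion of treated children with any clinical bleeding event of any grade. Ask about bleeding at each scheduled evaluation and record it on the existing adverse-event form. Report platelet count, PT, PTT, INR and fibrinogen separately as laboratory results, and state that the scheduled tests do not assess platelet function. Replace the assertion of safety with the estimate and its exact confidence interval; the interval method can sit in the statistical analysis plan.

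The cost is revised outcome wording, one case-report question per evaluation, and a less favourable safety statement at the end. The change needs no new test and leaves dosing and clinical management as they are.

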# Omegaven® Possible Adverse Events

CLINICAL							
GRADE I	GRADE II	GRADE III - SAE	GRADE IV - SAE				
(MILD)	(MODERATE)	(SEVERE)	(POTENTIALLY				
, , ,	, , , , , , , , , , , , , , , , , , ,	,	LIFE				
			THREATENING/				
			DEATH)				
Phlebitis	Hypotension	Bowel obstruction	Uncontrolled				
			bleeding				
Fever	Hypertension	Sepsis syndrome	Anaphylaxis				
Fishy taste	Urinary tract		Shock				
	infection						
Chills	Poor growth		Death				
Flushing	Priapism						
Cyanosis							
Nausea/Vomiting							
Dehydration							
Rash							
LABORATORY							
Hyperglycemia	Anemia	Sepsis	Coagulopathy				
Hypertriglyceridemia	Leukopenia						
Essential fatty acid	Thrombocytopenia						
deficiency	_						
Electrolyte	Abnormal liver						
abnormalities	function tests						
	Positive urine						
	culture

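### The bleeding safety outcome counts only *unexpected* events, leaves the word undefined, and so lets foreseeable bleeds be read out of it after the event

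*Protocol*

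**What the plan says.** **Outcome.** The section Definition of Primary and Secondary Outcomes/Endpoints expects PN with Omegaven to be safe "with respect to the risk of unexpected bleeding/coagulopathies", judged from the weekly and monthly evaluations. Neither that section nor any other in the protocol says what makes a bleed or a coagulopathy unexpected.

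**Foreseen effects.** Under Side effects: "The infusion of Omegaven® can lead to a prolonged bleeding time and an inhibited platelet aggregation". The same effects appear under Risks and Discomforts. The overall risk summary repeats them ("Prolonged bleeding times and inhibition of platelet aggregation are a potential risk") and singles out children who already have a coagulopathy or take an anticoagulant. The Coagulopathy paragraph under Dose Modification tells the team to consider sepsis and deteriorating liver function as other sources.

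**Action.** The Data and Safety Monitoring Plan lists, among the reasons for dose reduction, "or evidence of bleeding", with no qualifier.

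**Recording and grading.** The adverse event section has the investigator record every adverse event with its severity, relationship to study drug and action taken, and refers to the adverse event table for severity. That table is headed "Omegaven® Possible Adverse Events". Its only bleeding entry is "Uncontrolled" bleeding, at Grade IV. Its laboratory part lists "Coagulopathy" at Grade IV and thrombocytopenia at Grade II.

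**The concern.** An outcome that is meant to show whether a drug is safe for haemostasis should count the haemostatic events that occur. This one counts a subset, chosen by an undefined adjective. The events most open to exclusion are those the protocol itself anticipates: bleeds in children with failing livers, on a drug described as impairing platelet function.

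The study is non-randomized and open-label, so whoever classes a bleed as expected or unexpected knows the treatment and may have a view on its cause. With no definition fixed beforehand, that classification decides whether the event counts. The bias could run towards the conclusion that the outcome sentence already asserts, namely that the treatment is safe.

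**Working it through.** The protocol states no bleeding rate, margin or error level, so it has no figure to reproduce. The check compares the passages.

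**Step 1. Which events does each passage cover?**

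| Place in the protocol | Events covered | Qualifier |
|---|---|---|
| Secondary outcome | Bleeding and coagulopathies | *Unexpected*, undefined |
| Specific aims | Effect on coagulation profiles | None; bleeding not mentioned |
| Data and Safety Monitoring Plan | Evidence of bleeding | None |
| Adverse event section | All adverse events | None |
| Adverse event table | Bleeding, once, at Grade IV | *Uncontrolled* |
| Laboratory monitoring schedule | PT, PTT, INR, fibrinogen, platelets, at baseline and at each stage | None |

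The outcome is the only place where expectedness decides whether an event is counted.

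**Step 2. What does *unexpected* admit?** The text leaves at least three readings open.

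| Reading | Bleed attributed to the drug | Bleed attributed to liver disease or sepsis |
|---|---|---|
| Not foreseen from the known effects of drug and disease | Out | Out |
| Not explained by the child's own condition or a procedure | In | Out |
| Any clinical bleed, since only haemostatic measures are foreseen | In | In |
| Word deleted | In | In |

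Two of the three readings drop a foreseeable class of bleeds, and the protocol does not choose between them. Only a severe hemorrhagic disorder excludes a child, so children with a milder coagulopathy or on an anticoagulant may enrol. Their bleeds would be the easiest to call expected, although the risk summary names these children as the ones at particular risk.

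**Step 3. Do the laboratory tests close the gap?** Only in part. The schedule contains the five coagulation-related tests in the table above. It contains neither bleeding time nor platelet aggregation, the two effects named for the drug. Clinical bleeding is therefore an important way for those effects to show in this outcome, and it is subject to the filter.

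**Step 4. Illustration of size.** Assume three bleeds, all classed as expected. The count of three is an assumption. Recruitment of 3 to 5 children a year for five years gives 3 × 5 = 15 to 5 × 5 = 25 children; the protocol plans 20 to 25. Exact (Clopper-Pearson) 95% limits:

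- No events: upper limit = 1 − 0.025^(1/n). For n = 25 this is 13.7%; for n = 15 it is 21.8%.
- Three events: lower limit = the 0.025 quantile of Beta(3, n − 2); upper limit = the 0.975 quantile of Beta(4, n − 3).

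| Children | All bleeds counted | Expected bleeds dropped |
|---|---|---|
| 25 | 3/25 = 12% (2.5% to 31.2%) | 0/25 (0% to 13.7%) |
| 15 | 3/15 = 20% (4.3% to 48.1%) | 0/15 (0% to 21.8%) |

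In a study of this size, the classification of a few events changes the reported result.

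**The case against.** A reader might infer that an ordinary drug-related bleed falls outside both the outcome and the adverse event record. The protocol does not support that. Every adverse event is to be recorded, graded and assessed for relatedness, and the action taken with study drug is documented. The adverse event table lists possible events, is not stated to be exhaustive, and includes coagulopathy and thrombocytopenia. This part of the objection stands in full: bleeds are not left unrecorded, and dose reductions for them would be visible in the case report forms.

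It is also fair to say that the named drug effects are bleeding time and platelet aggregation, not clinical bleeding. The protocol reports that no adverse effects attributable to Omegaven have been seen and that earlier use was not associated with coagulopathy. On that footing a drug-related bleed could well be called unexpected and be counted. This stands as far as it goes: the exclusion is one reading, not a rule. It does not rescue the wording, because an outcome whose content depends on the reader is badly fixed. A bleed attributed to liver disease can still be dropped.

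A precautionary dose trigger may properly be wider than an outcome, so the unqualified bleeding trigger is not in itself a contradiction. The aim on coagulation concerns laboratory profiles, so the outcome cannot be said to exclude bleeds that the aim is about.

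Finally, operational definitions are often left to the statistical analysis plan, which is not shown here. But the restriction stands in the protocol's own outcome sentence. A later plan could define the word, but it would have to work within the restriction unless the protocol changes.

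**Conclusion.** The concern holds as a fault of endpoint definition. The bleeding and coagulopathy outcome is limited by an undefined word, in an open-label single-arm study whose protocol foresees impaired haemostasis from both drug and disease. Foreseeable bleeds can be removed from the outcome after the event, although they are recorded as adverse events and can prompt dose reduction.

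It would go too far to conclude that the protocol excludes drug-related bleeds outright, or that it would conceal them. The first depends on one reading of *unexpected*; the second is contradicted by the adverse event recording rules.

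The size is unknown. The intervals above show only how sensitive a study of 15 to 25 children is to the classification; they rest on an assumed three bleeds, all classed as expected. The conclusion itself needs no event rate. It rests on the wording and on the absence of a definition in the protocol. The change is worth making before the outcome is analysed.

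**What to change.** **Outcome sentence.** Delete *unexpected*. Report, by child, every on-treatment clinical bleeding event whatever its cause, and the change from baseline in PT, PTT, INR, fibrinogen and platelets, which the laboratory schedule already collects. Show relatedness to study drug and likely cause beside each event, as description and not as a condition for counting it.

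**Adverse event table.** Its single bleeding entry should be reconciled by the sponsor with the unqualified bleeding trigger in the Data and Safety Monitoring Plan and with the rule in the adverse event section that temporarily halts treatment for moderate or severe events that may be related. Because grade affects treatment there, how lesser bleeds are graded is a clinical decision for the sponsor; no grade or treatment rule is proposed here.

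**Cost.** One outcome sentence, and a reconciliation of three passages. No new tests are needed. The reported bleeding rate may look less favourable, since bleeds due to the underlying disease will be counted too; the cause shown alongside lets readers see this.
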